This study is being conducted to address a Food and Drug Administration (FDA) postmarketing requirement to conduct a single-arm prospective and retrospective observational study of pregnant women exposed to Repatha to evaluate fetal and infant outcomes through the first year of life. This study will estimate the proportion of pregnancy and maternal complications, adverse events in the developing fetus and neonate, and adverse events in the infant through the first year of life using data from pre-existing reports within Amgen's Global Safety Database.

- Research Question and Objective(s)

Objectives	Endpoints
Primary	
Among women exposed to Repatha during pregnancy, to estimate the proportion of: 
- Pregnancy and maternal complications- Adverse events in the developing fetus and neonate- And among their infants, adverse events for the first year of life.	
• Number of cases reporting pregnancy and maternal complications.• Pregnancy Outcomes: Number of cases reporting live full-term births, spontaneous abortion, elective abortion, stillbirth, and premature delivery.• Infant Outcomes: Number of cases reporting adverse events including complications, medical problems or congenital anomalies at birth.• Number of cases reporting adverse events at 6 months and 12 months.

- Hypothesis(es)/Estimation

This is an estimation study. No formal hypothesis will be tested.

- Study Design/Type

This is a Global prospective and retrospective observational case series of pregnant women exposed to Repatha during pregnancy and their infants through the first year of life.

- Study Population or Data Resource

Case finding through the Amgen Global Safety Database and other post marketing sources which include: spontaneous (including regulatory authority and literature), solicited (ie, patient support programs and market research), and postmarketing non-interventional studies. Retrospectively, data will be extracted from pre-existing postmarketing reports obtained from Amgen's Global Safety Database for women exposed to Repatha during pregnancy and their infants between July 2015 and the approval date of this protocol. Prospectively, from approval date of this protocol through July 2025, secondary data from postmarketing reports will be analyzed for women who have been exposed to Repatha during their pregnancy and their infants. Patients who refused consent will be excluded.

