8.3.2 Outcome Assessment

Pregnancy outcomes include the number of women reporting pregnancy or maternal complications, as well as, the number reporting:

- Live full-term births
- Spontaneous abortion defined as non-deliberate fetal death which occurs prior to 20 completed weeks post-LMP
- Elective abortion defined as deliberate termination of pregnancy at any time in gestation
- Fetal death/Stillbirth defined as non-deliberate fetal death anytime in gestation at or after 20 completed weeks post-LMP
- Premature delivery defined as live birth prior to 37 weeks gestation as counted from LMP (eg, ultrasound adjusted date or Ballard's score)

Outcomes related to pregnancy and maternal complications will be assessed with a Pregnancy Questionnaire (a sample form included in [Appendix C](#)). Outcomes for live births will be assessed with a Post Due Date Questionnaire (a sample form included in [Appendix D](#)) from the Amgen Global Safety Database.

The number of infants with adverse events including complications, medical problems or congenital anomalies at birth will be assessed with a Post Due Date Questionnaire (a sample form included in [Appendix D](#)) from the Amgen Global Safety Database.

Major malformations or birth defects are defined as abnormalities incompatible with life or requiring medical/ surgical intervention. The term minor birth defect generally refers to minor physical anomalies with less clinical importance that represent deviations from what is considered normal and do not have obvious medical, surgical, or cosmetic consequences. Major birth defects identified up to 1 year of age by the mother or the healthcare provider will be included in the primary analysis. Major structural birth defects may be reported by the mother, a family member or her or her child's HCP via medical records. If a major malformation is reported the medical record will be adjudicated by a physician with expertise in teratology, pediatrics, and dysmorphology. Defects will be

classified using the Center for Disease Controls (CDC) criteria (CDC 2017.:
<https://www.cdc.gov/ncbddd/birthdefects/macdp.html>).

Infant outcomes are the number of cases reporting adverse events at 6 months and 12 months and may include whether they have not followed growth curves or met development milestones as expected for chronological age. These outcomes will be assessed with an Infant Questionnaire (a sample form included in [Appendix E](#)).

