8.7.2.3.3 Analysis of the Primary, Secondary, and Exploratory Endpoint(s)

All analyses will be descriptive. These cases constitute a case series, thus line listings of pregnancy and maternal complications, pregnancy outcomes, infant outcomes and adverse events will be summarized along with tabulations of the numbers and frequencies of events by category of report: numbers who did not provide consent for follow-up, timing of exposure (first, second, or third trimester), and indication for use of the medication. Collection of exposure and outcome information in this group provides additional evidence on the safety of Repatha use during pregnancy. The denominator is the number of pregnant women exposed to Repatha during pregnancy and the numerator is the number with the outcome.

The proportion of infants with adverse events including complications, medical problems or congenital anomalies at birth will be assessed in infants of women exposed to Repatha during pregnancy with corresponding 95% confidence intervals. The proportion of infants with adverse events at 6 months and 12 months of age will be assessed. All adverse events among mothers who have received Repatha at any time during the pregnancy will be summarized including the proportion with pregnancy and maternal complications. To assess events in the developing fetus and neonate in women exposed to Repatha during pregnancy, the proportion of pregnancies resulting in spontaneous abortions, elective abortions, fetal death/ stillbirths and premature delivery will be presented, along with corresponding 95% confidence.

If the available safety information relevant to exposure during pregnancy represents a safety signal, the signal will be further evaluated through the Amgen safety governance structure and, if deemed necessary, escalated for consideration of changes to the Reference Safety Information (eg, USPI) as well as other forms of risk communication (eg, Dear Healthcare Provider Letters).

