Appendix C. Initial Pregnancy Questionnaire – Mother

Safety Database #

INITIAL PREGNANCY QUESTIONNAIRE (MOTHER)

You may return completed form to Amgen Office Fax or Email:

[contact] Email: [contact]

Section 1 – Reporter Information

Reporter: Mother Health Care Professional Other _____ Parent exposed to product? Mother Father
 Name _____ Phone () _____ Fax () _____
 Email _____ Address _____ City _____
 State/Province _____ Zip/Postal Code _____ Country _____
 *Did the patient sign the Authorization for Release of Medical Information? Yes No

In the event your contact information changes, please provide a back-up contact (for example a close relative or friend who does not live with you) who we may reach in an effort to contact you.

Relationship to patient: _____
 Name _____ Phone () _____ Fax () _____
 Email _____ Address _____ City _____
 State/Province _____ Zip/Postal Code _____ Country _____

Section 2 – Mother Current Pregnancy Information

Mother's Initials: _____ Date of birth: (if permitted to provide by local laws) _____ Date of last menstrual period: _____
 Age: _____ years Day _____ Month _____ Year _____ Day _____ Month _____ Year _____
 Number of fetuses: _____ Estimated date of delivery: _____
 Day _____ Month _____ Year _____

Relevant Laboratory Tests & Procedures

Test Name	Test Date (dd/mm/yr)	Test Result

Section 3 – Mother Prenatal Medication History

Please list all medications (prescription and over-the-counter [include vitamins, herbal medications, etc.] and vaccines, taken by the mother within 3 months prior to or during pregnancy.

Amgen Product Used	Dose	Route (e.g. oral, subcutan.)	Frequency (e.g. daily, weekly)	Date Drug Started (dd/mm/yy)	Date Drug Stopped (dd/mm/yy)	Weeks of Pregnancy When Drug Taken (e.g. wk 28–wk 32)	Indication for Treatment
Resumed (if applicable)							

Amgen Product Lot Number _____ Lot Number Not Known

Safety Database #

List any other medications used within 3 months prior to or during the pregnancy

Medications/Drugs	Dose	Route (e.g. oral, subcutaneous)	Frequency (e.g. daily, weekly)	Date Drug Started (dd/mm/yy)	Date Drug Stopped (dd/mm/yy)	Indication for Treatment

Section 4 – Pregnancy Complication and Adverse Event Information

If the **mother** experienced any pregnancy complications (e.g. preeclampsia, gestational diabetes, placenta previa, etc.) please complete the following:

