6 TO 8 WEEKS POST DUE DATE QUESTIONNAIRE (MOTHER)

Section 1 – Reporter Information

Reporter: Mother Health Care Professional Other _____

Any change in the reporter contact information? Yes No If yes, please provide updated contact information:

Name _____ Phone () _____ Fax () _____

Email _____ Address _____ City _____

State/Province _____ Zip/Postal Code _____ Country _____

Section 2 – Mother Prenatal Medication History

Please provide any additional medication information for medicines used during your pregnancy not previously reported. For example, if you resumed or discontinued the Amgen Product or any other medications during the pregnancy (include vitamins, folic acid, herbal medications, and vaccines).

Medications/Drugs	Dose	Route (e.g. oral, subcutaneous)	Frequency (e.g. daily, weekly)	Date Drug Started (dd/mm/yy)	Date Drug Stopped (dd/mm/yy)	Indication for Treatment

Section 3 – Mother Pregnancy Complications and/or Adverse Event Information

Pregnancy Complication or Adverse Event (e.g. preeclampsia, gestation diabetes)	Date the Complication or Event Started (dd/mm/yy)	Date the Complication or Event Resolved (dd/mm/yr)	Outcome (for example: resolved, not resolved, unknown, other, etc.)

Amgen Proprietary - For Internal Use Only

6 to 8 Weeks Post Due Date Questionnaire (Mother)

Version 1. Effective: 16 September 2015

Page 1 of 2

Safety Database # [case_id]

6 TO 8 WEEKS POST DUE DATE QUESTIONNAIRE (MOTHER) *continued*

Section 4 – Mother Current Pregnancy Outcome (if applicable)

Date pregnancy ended: _____ Weeks of pregnancy at delivery (or if the outcome was a
Day Month Year loss of pregnancy): _____ weeks

Pregnancy Outcome (please check the appropriate box below)

- Live birth
 - Number of infants _____ (1: single, 2: twins, etc.)
(If multiple births: Please provide all information for each infant in the additional information text box below:)
- Pregnancy loss (miscarriage)
- Stillbirth
- Termination
 - Due to health issue (mother or baby)
 - For voluntary reason
 - Other (please specify): _____

If live birth: Gender: Male Female

Length: _____ cm/inches Birth weight: _____ gram/lb Head circumference: _____ cm/inches

Did the baby have any complications/medical problems/congenital anomalies (birth defects)? Yes No

If yes, please provide specific information below.

Additional Information on pregnancy outcome:

Section 5 – Reporter Signature

Signature of person completing questionnaire: _____ Date: _____

Please print name: _____

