Appendix E. 6- and 12-month Infant Questionnaire

Mother Safety Database #	
Infant Safety Database #	

SIX AND TWELVE MONTH
INFANT QUESTIONNAIRE

From: {Title} {First Name} {Last Name} {Company Name} {Country}	[today]
To:[reporter_first_name:corresp_contact] [reporter_last_name:corresp_contact]	

Event: Pregnancy	Product: [product_name]:[1]
AER#: [case_id]	Reply Due By: {Due Date}

Dear [reporter_first_name:corresp_contact] [reporter_last_name:corresp_contact],

Thank you for reporting your [patient_initials] pregnancy while on [product_name:first_suspect] ([generic_name:first_suspect]) therapy. Please send the completed questionnaire with requested information to the address, email or fax below.

Kindly note the following attachments:

- **SIX AND TWELVE MONTH INFANT QUESTIONNAIRE**

Respectfully Yours,

{Title} {First Name} {Last Name}
{Company Name} {Country}
Email: {email}
Fax: {fax}
Phone: {phone}

SIX AND TWELVE MONTH INFANT QUESTIONNAIRE

Mother Safety Database #

Infant Safety Database #

You may return completed form to Amgen Office Fax or Email:

Section 1 – Reporter Information

Reporter: Mother Father Health Care Professional (HCP) Other _____

Section 2 – Infant Healthcare Provider (HCP) Information

May Amgen contact the HCP for medical information regarding your child? Yes No

If yes, please provide contact information:

Name _____ Phone () _____ Fax () _____

Email _____ Address _____ City _____

State/Province _____ Zip/Postal Code _____ Country _____

Section 3 – Infant Medical Health Information

List any other medications/drugs (include vitamins and over-the-counter medications taken by the child)

Medications/Drugs	Dose	Route (e.g. oral, subcutaneous)	Frequency (e.g. daily, weekly)	Date Drug Started (dd/mm/yy)	Date Drug Stopped (dd/mm/yy)	Indication for Treatment

Has the infant had any abnormal screening tests? Yes No If yes, please explain:

Has the infant followed growth curves and developmental milestones as expected for chronological age?

Yes No If no, please explain:

Has the infant had any illnesses or persistent health problems? Yes No If yes, please explain:

Section 4 – Reporter Signature

Signature of person completing questionnaire: _____ Date: _____

Please print name: _____ Title and specialty if HCP _____

Approval Signatures

Document Name: Protocol-Published Original Evolocumab 20200408

Document Description:

Document Number: CLIN-000272100

Approval Date: 16 Jul 2021

Type of Study Protocol: Original

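### The maternal forms cannot separate 'no complication' from 'not answered', which pulls the maternal-complication proportion down by an unknown amount

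*Protocol*

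**What the plan says.** The endpoint for the first objective is "Number of cases reporting pregnancy and maternal complications" (Protocol, Abstract, Research Question and Objectives). Section 8.3.2 names the instrument: "Outcomes related to pregnancy and maternal complications will be assessed with a Pregnancy Questionnaire", with Appendix C as the sample form. Section 8.7.2.3.3 gives the estimator: "The denominator is the number of pregnant women exposed to Repatha during pregnancy and the numerator is the number with the outcome".

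Maternal complications are asked for in two places:

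- **Appendix C, Section 4** gives a table to fill in if the mother "experienced any pregnancy complications (e.g. preeclampsia, gestational diabetes, placenta previa, etc.) please complete the following".
- **Appendix D** has "Section 3 – Mother Pregnancy Complications and/or Adverse Event Information" as a heading, with a table beneath it and no lead-in sentence.

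Neither place has a Yes/No or 'none' box. Other items do. The newborn item in Appendix D, Section 4 reads "Did the baby have any complications/medical problems/congenital anomalies (birth defects)? Yes No", and Appendix C, Section 7 has the same question with the same boxes. The 6- and 12-month form (Appendix E, Section 3) asks "Has the infant had any illnesses or persistent health problems? Yes No If yes, please explain".

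Section 8.7.2.2 holds that, since no association is assessed, missing or incomplete data will not bias the results, though they may affect accuracy. The same section says that self-report may lead to overestimation. Sensitivity analyses are marked not applicable (Section 8.7.2.4 and its subsections).

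**The concern.** A proportion needs two counts: women with the event, and women in whom the event was looked for. The maternal forms record only the first. A blank table may mean that nothing happened, that the section was overlooked, or that the woman chose not to answer, and the form gives no means of telling these apart.

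An analysis plan can decide how to score a blank, but it cannot supply an answer that the form did not request. The forms are part of this protocol, so the gap belongs to this document. It affects the first-listed primary objective, which is summarised in each annual report to the regulator and in the final report.

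**Working it through.** **No figure to reproduce.** The protocol states no sample size, expected rate or non-response rate. All rates below are assumptions, used only to show direction and scale.

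**Step 1. Effect of blanks alone.**
- p = true proportion of women with a complication (assumed 10%, 20%, 30%).
- s = share of women with a complication for whom it appears in no source, neither form nor any other report (assumed 10% to 30%).
- The denominator is all exposed women, as in Section 8.7.2.3.3. A blank adds nothing to the numerator.

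Observed proportion = p × (1 − s); bias = −p × s.

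| True p | s = 10% | s = 20% | s = 30% |
|---|---|---|---|
| 10% | 9% | 8% | 7% |
| 20% | 18% | 16% | 14% |
| 30% | 27% | 24% | 21% |

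Over this grid the loss is 1 to 9 percentage points. At p = 20% and s = 20% it is 0.20 × 0.20 = 4 points. This mechanism alone can only lower the proportion.

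**Step 2. Adding the over-reporting that Section 8.7.2.2 expects.** Let r be how many times more likely women with an event are to enter the series. The proportion within the series becomes q = r × p / (r × p + 1 − p), and the observed value is q × (1 − s). With p = 20% and s = 20%:

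- r = 1.25: q = 0.25 / 1.05 = 23.8%; observed 0.238 × 0.8 = 19.0%, below the truth.
- r = 1.5: q = 0.30 / 1.10 = 27.3%; observed 0.273 × 0.8 = 21.8%, above the truth.

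The two errors cancel when s = 1 − p/q. At p = 20% that is s = 16% for r = 1.25, 27% for r = 1.5 and 40% for r = 2. The documents give neither r nor s, so the sign of the net error cannot be determined.

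**Step 3. What can be computed from forms already returned.** Let a = women with an event from any source, c = women with a recorded negative, b = women with neither.

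- Blanks as 'no': a / (a + b + c).
- Blanks excluded: a / (a + c).

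The current forms have no box that produces c. If no negative is recorded elsewhere (a written 'none', or a provider's report), c = 0 and the second figure is a / a = 100% whatever the truth. The two results can therefore lie far apart, and the gap shows how little the existing forms determine.

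**The case against.** Several points on the other side stand.

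- **Other routes of capture.** Complications are asked about on two forms at different times. Appendix C, Section 5 also invites illnesses during pregnancy. Both maternal forms ask permission to contact healthcare providers. Sections 8.4 and 8.6 describe follow-up and further attempts with consent, and the initial safety report may already state an event. A reader might infer that a skipped table is lost for good; the documents do not support that. However, these routes mainly recover events. None is described as recording a negative answer or as triggered by a blank table.
- **No written scoring rule.** A reader might infer that the protocol orders blanks to be scored as 'no complication'. It does not. That scoring follows from the all-exposed denominator, and an analysis plan not shown here could handle blanks otherwise.
- **Net direction.** A reader might infer that the reported proportion will be too low. Section 8.7.2.2 names over-reporting, and Section 8.7.5.1.1 adds that women without complications may be less likely to consent or to stay in follow-up. Step 2 shows that either sign is possible.
- **The newborn and infant endpoints are not immune.** If their stated denominator also includes everyone, an unanswered box there counts as no event too. The difference is that the unanswered box can be seen and counted.
- **The conditional wording is in Appendix C only.** Appendix D has just the table, but leaves the same ambiguity.
- **Limited reach of a form change.** These are sample forms from routine safety follow-up, and data go back to July 2015. A new box cannot repair past cases.

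These points narrow the claim but do not remove it. Two opposing errors of unknown size make the proportion harder to interpret, and this one can be reduced for future cases.

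**Conclusion.** The point holds in limited form. For the first primary objective, the maternal forms do not distinguish 'none' from 'not answered', and with all exposed women as denominator this pulls the proportion down by an unknown amount. The 4-point loss at an assumed true 20% and 20% of events missing from every source illustrates scale; it is not an estimate. It assumes that blanks stay in the denominator and add nothing to the numerator. The net direction of error in the reported proportion is undetermined.

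The Section 8.7.2.2 statement that missing data cannot cause bias because no association is assessed is wrong for this endpoint: a descriptive proportion is biased when unrecorded events are counted as absent. The same section's warning about overestimation already concedes that a descriptive proportion can be distorted.

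**What to change.** 1. **Forms, for future cases.** Above the table in Appendix C, Section 4 and in Appendix D, Section 3, add: *Any pregnancy complication or maternal adverse event? Yes / No / Unknown*.
2. **Main estimate.** Report the proportion among women with a Yes or No answer, or with an event known from another source, and print the number not stated beside it. This is unbiased only if not answering is unrelated to the outcome; if women with events answer more readily, it will run high.
3. **Forms already returned.** Report blank tables as 'not stated', and show the proportion with blanks as 'no' and with blanks excluded, as a range. Neither end is unbiased if non-answer depends on outcome. State how many recorded negatives the second figure rests on, because with none it is 100% by construction.
4. **Section 8.7.2.2.** Replace the statement that missing data will not cause bias with one saying that unanswered complication items can lower this proportion, that selective reporting can raise it, and that the net effect is unknown.

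**Cost.** A small revision to two routine safety forms, which are worded for the sponsor's products in general and so may need agreement beyond this study, plus an extra row in the tables. Section 11.1 sends protocol amendments to the regulator before any change in conduct. Items 3 and 4 need no form change. A 'not stated' category will remain for the retrospective cases.

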Appendix D. 6 to 8 Weeks Post Due Date Questionnaire – Mother

Safety Database #

You may return completed form to Amgen Office Fax or Email:

6 TO 8 WEEKS POST DUE DATE QUESTIONNAIRE (MOTHER)

Section 1 – Reporter Information

Reporter: Mother Health Care Professional Other _____

Any change in the reporter contact information? Yes No If yes, please provide updated contact information:

Name _____ Phone () _____ Fax () _____

Email _____ Address _____ City _____

State/Province _____ Zip/Postal Code _____ Country _____

Section 2 – Mother Prenatal Medication History

Please provide any additional medication information for medicines used during your pregnancy not previously reported. For example, if you resumed or discontinued the Amgen Product or any other medications during the pregnancy (include vitamins, folic acid, herbal medications, and vaccines).

Medications/Drugs	Dose	Route (e.g. oral, subcutaneous)	Frequency (e.g. daily, weekly)	Date Drug Started (dd/mm/yy)	Date Drug Stopped (dd/mm/yy)	Indication for Treatment

Section 3 – Mother Pregnancy Complications and/or Adverse Event Information

Pregnancy Complication or Adverse Event (e.g. preeclampsia, gestation diabetes)	Date the Complication or Event Started (dd/mm/yy)	Date the Complication or Event Resolved (dd/mm/yr)	Outcome (for example: resolved, not resolved, unknown, other, etc.)

Amgen Proprietary - For Internal Use Only

6 to 8 Weeks Post Due Date Questionnaire (Mother)

Version 1. Effective: 16 September 2015

Page 1 of 2

Safety Database # [case_id]

6 TO 8 WEEKS POST DUE DATE QUESTIONNAIRE (MOTHER) *continued*

Section 4 – Mother Current Pregnancy Outcome (if applicable)

Date pregnancy ended: _____ Weeks of pregnancy at delivery (or if the outcome was a
Day Month Year loss of pregnancy): _____ weeks

Pregnancy Outcome (please check the appropriate box below)

- Live birth
 - Number of infants _____ (1: single, 2: twins, etc.)
(If multiple births: Please provide all information for each infant in the additional information text box below:)
- Pregnancy loss (miscarriage)
- Stillbirth
- Termination
 - Due to health issue (mother or baby)
 - For voluntary reason
 - Other (please specify): _____

If live birth: Gender: Male Female

Length: _____ cm/inches Birth weight: _____ gram/lb Head circumference: _____ cm/inches

Did the baby have any complications/medical problems/congenital anomalies (birth defects)? Yes No

If yes, please provide specific information below.

Additional Information on pregnancy outcome:

Section 5 – Reporter Signature

Signature of person completing questionnaire: _____ Date: _____

Please print name: _____

Title and specialty if HCP: _____

For consumers/patients only. Please provide contact information for your and your child's HCPs
May Amgen contact your HCP? Yes No

Health Care Provider for the pregnancy/delivery:

Name _____ Phone () _____ Fax () _____

Email _____ Address _____ City _____

State/Province _____ Zip/Postal Code _____

Health Care Provider who is prescribing the Amgen product:

Name _____ Phone () _____ Fax () _____

Email _____ Address _____ City _____

State/Province _____ Zip/Postal Code _____

Health Care Provider for the child:

Name _____ Phone () _____ Fax () _____

Email _____ Address _____ City _____

State/Province _____ Zip/Postal Code _____ Country _____

